MI-SI Training. Training will consist of sixteen hours. It will consist of 8 hours of training in general MI followed by eight hours of MI-SI training. Training modalities include listening to power-point presentations, selected readings from the MI text  and the MI-SI manual (included in Appendix), MI exercises, and listening to and discussing recorded examples of MI-SI. The PI will observe the first two interviews to ensure that therapists meet MITI fidelity criteria and provide corrective feedback. Additional training activities will be scheduled as necessary.

MI-SI Supervision. An RCT evaluating methods for training MI clinicians found that ongoing coaching and/or feedback is needed to maintain proficiency in MI.  The PI will provide weekly supervision for MI-SI clinicians, focusing on promoting the fidelity of MI-SI by discussing

difficult cases, listening to and discussing recorded MI-SI interviews, and reviewing MI materials and publications.

**Interview Coding and Training.** MI-SI sessions will be recorded and coded for fidelity using the MITI,  which requires specialized training.

MITI Coding and Training. The MITI is a behavioral coding system that is used to code 20-minute samples of tape for adherence to MI principles (e.g. empathy, autonomy support) and use of specific MI techniques (e.g. reflections, open questions). Summary values from coded interviews will be used to assess fidelity,  and provide material for supervisory sessions. A random selection of interviews will be double-coded and inter-rater reliability will be computed using inter-class correlation coefficients. 

The PI will provide MITI training to the research assistants who are coding the MI-SI therapy sessions. The protocol that will be used is identical the one use by [name]., an MI Training expert who trained coders for Project MATCH,  and trained the PI. Training will consist of eight hours and include reviewing the MITI coding scale, coding MI interviews and comparing the codes to "gold standard" codes available on the MI website,  and coding recordings of MI-SI interviews. Coders will be considered reliable when they achieve reliabilities of good or better (ICC > .60) on 80% of MITI codes. 

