MI-SCOPE Coding and Training. The Sequential Code for Observing Process Exchanges (SCOPE),  will be adapted for use with suicidal clients. SCOPE is a coding scheme developed to examine sequential therapeutic interactions between clinicians and clients to study the psychotherapy process and its relation to treatment outcome.  It includes the codes used for the MITI, and additional codes for clinicians (e.g., confrontation, emphasize control, feedback), and clients (e.g., follow, ask, commitment). We will adapt the MI-SCOPE by adding codes for living and suicide talk, and other suicide-related statements. Interviews are transcribed, and both transcripts and audio recordings are used for coding. A random selection of interviews will be double-coded and inter-rater reliability will be computed using inter-class correlation coefficients. 

The PI will also provide MI-SCOPE training to the research assistants who are coding the therapy sessions. The MI-SCOPE protocol is identical to that used by the developers of MI-SCOPE.  Because the MI-SCOPE is more intensive, training will consist of sixteen hours and include reviewing the MI-SCOPE coding scale, coding MI-SI interviews and comparing the codes to "gold standard" codes that the PI derives. Coders will be considered reliable when they achieve reliabilities of good or better (ICC > .60) on 80% of MITI codes. 

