### **Aim 3:** To evaluate improvements during hospitalization.

Exploratory Hypothesis 3: Participants who receive MI-SI plus TAU will report greater reductions in SI during hospitalization, than participants who receive TAU alone.

Exploratory Hypothesis 4: In participants who receive MI-SI plus TAU, in-session living talk will be positively associated with reductions in SI during hospitalization.

Exploratory Hypothesis 5: In participants who receive MI-SI plus TAU, in-session suicide talk will be negatively associated with reductions in SI during hospitalization.

Exploratory Analyses 3-5: Data will be analyzed using GLMM to account for repeated measures within subjects  with a focus on within subject decreases in SI (assessed with SSI scores). A minimum of two GLMMs will be used to examine the effect of MI-SI on the severity of SI at 2-3 and 3-5 days after the baseline assessment, the strength of in-session living and suicide talk and the severity of SI at 2-3 and 3-5 days after the baseline assessment. We will also examine the associations between in-session living and suicide talk on the severity of SI over 1, 3, and 6 months follow-up.

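### The MI-SCOPE coder-qualification rule is stated on MITI codes, so it does not test the living-talk and suicide-talk codes used in Exploratory Hypotheses 4 and 5

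*Combined protocol and SAP*

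**What the plan says.** All references are to the combined protocol and SAP.

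- **MITI Coding and Training.** The MITI is applied to session samples to rate "adherence to MI principles (e.g. empathy, autonomy support) and use of specific MI techniques (e.g. reflections, open questions"). Coders of this instrument qualify on an ICC above .60 for 80% of MITI codes.
- **MI-SCOPE Coding and Training, content.** Of the MI-SCOPE the protocol says "It includes the codes used for the MITI, and additional codes for clinicians", and for clients. For this study, "We will adapt the MI-SCOPE by adding codes for living and suicide talk, and other suicide-related statements".
- **MI-SCOPE Coding and Training, qualification.** "Coders will be considered reliable when they achieve reliabilities of good or better (ICC > .60) on 80% of MITI codes". The wording is the same as in the MITI paragraph.
- **MI-SCOPE Coding and Training, other checks.** The sixteen hours of training include "comparing the codes to 'gold standard' codes that the PI derives". Also, "A random selection of interviews will be double-coded and inter-rater reliability will be computed using inter-class correlation coefficients".
- **Aim 3 in the Analytical Plan.** Exploratory Hypothesis 4 is that "in-session living talk will be positively associated with reductions in SI during hospitalization"; Exploratory Hypothesis 5 is that "in-session suicide talk will be negatively associated with reductions in SI during hospitalization". The same talk variables are also to be related to suicidal ideation at 1, 3 and 6 months.

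**The concern.** The codes that decide whether an MI-SCOPE coder is ready are not the codes that will be analysed. Living talk and suicide talk are client-speech codes created for this study, whereas the MITI is described as rating adherence to MI and use of MI techniques. A coder could therefore meet the stated criterion with poor agreement on both talk codes.

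The stake is the interpretation of the talk analyses. Random coding error in a predictor pulls its association with the outcome towards zero, so a weak or null result could partly reflect the coding. The protocol's Study of Speech summary says the trial is meant to supply data for later work on these proposed mechanisms, so the quality of this measurement carries forward beyond the trial.

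**Working it through.** The protocol gives no reliability or power figure for the talk analyses, so there is none to reproduce. The check compares code sets and then illustrates the possible size.

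**1. What the rule tests and what the analysis uses**

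| | Code set |
|---|---|
| Tested by the MI-SCOPE qualification rule | MITI codes |
| Contained in the MI-SCOPE | MITI codes plus further clinician and client codes |
| Added by this study | Living talk, suicide talk, other suicide-related statements |
| Predictors in Exploratory Hypotheses 4 and 5 | Living talk, suicide talk |

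The predictors lie in the third row and the rule covers only the first. The lowest ICC that the rule permits on a talk code is therefore unlimited: a coder near 0 on both could still qualify.

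**2. Would changing MITI to MI-SCOPE be enough?** Not fully. An 80% rule allows 20% of codes to fail. The number of codes is not given; if it were 10, 20 or 40, then 2, 4 or 8 could fail, and the talk codes could be among them.

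**3. Do the other checks close the gap?** Double-coding produces ICCs, but no sampling fraction, minimum, per-code report or action is stated. The comparison with gold-standard codes is part of training, and the only pass mark attached to it is the MITI rule.

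**4. Illustration of size**

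Inputs:
- n = 112 / 2 = 56 in the MI-SI arm (Power Analysis; equal allocation).
- One-sided .05, or .01 if exploratory analyses are reported with the primary RCT (Data Preparation).
- True r = .40 and ICCs of .90, .60 and .30: assumptions, not in the documents.

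Formulas: observed r = true r × √ICC; power = Φ(atanh(observed r) × √(n − 3) − z), with √53 = 7.280, z = 1.645 at .05 and z = 2.326 at .01.

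| ICC | Observed r | atanh × 7.280 | Power at .05 | Power at .01 |
|---|---|---|---|---|
| .90 | .379 | 2.908 | .90 | .72 |
| .60 | .310 | 2.332 | .75 | .50 |
| .30 | .219 | 1.621 | .49 | .24 |

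For example, at ICC .60: .40 × √.60 = .310; 2.332 − 1.645 = 0.687; Φ(0.687) = .75.

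Varying the assumed true r at ICC .60 and one-sided .05 gives power .53 for r = .30 and .91 for r = .50. With 45 participants, the per-arm number that the Power Analysis expects at 6 months, r = .40 and ICC .60 give .67.

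**The case against.** The strongest reply is that this is a copying slip in a minor part of the plan. The sentence is identical to the one closing the MITI paragraph, while the text around it concerns MI-SCOPE training, MI-SI interviews and gold-standard codes for the adapted scale. The intended word was probably MI-SCOPE. That is likely, but coders are certified on what is written, and the one-word correction would still let the talk codes fail within the 20% allowance. Asking for a separate pass on those codes is stricter than the protocol's general approach. It is justified here because they are new to this study and are the predictors.

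A reader might infer that a null result for Hypotheses 4 and 5 could not be told apart from unreliable coding. The documents do not support that: MI-SCOPE interviews are to be double-coded and ICCs computed, which is the evidence needed to tell the two apart. What is missing is narrower, namely a threshold, a report for the specific codes and a consequence.

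It is also fair to say that these hypotheses are exploratory and that the protocol states the study is not powered for them. That stands and limits the weight of the point. The power figures show how attenuation works and are not a shortfall against a planned target. They replace the planned GLMM on repeated SSI scores with a simple correlation, and they assume that all 56 participants have a coded session. In Pilot Study #1, 3 of 16 were discharged before the first session.

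**Conclusion.** The point holds in a limited form. As written, the MI-SCOPE qualification rule does not test the codes that supply the predictors in Exploratory Hypotheses 4 and 5 and in the talk analyses at 1, 3 and 6 months, and the planned double-coding has no threshold or action attached. This conclusion rests on the text alone and needs no numerical assumption.

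The size of any harm is unknown, because the documents give neither an expected ICC nor an expected association. Nothing in them shows that the talk codes will in fact be coded poorly. Under the assumed r of .40, moving from ICC .90 to .30 would cost about 41 points of power at one-sided .05 (.90 − .49) and about 48 points at .01 (.72 − .24).

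The primary SSI analysis does not use these codes and is unaffected. The wording should be corrected before session coding starts.

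**What to change.** In MI-SCOPE Coding and Training:

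1. Restate the qualification rule as ICC > .60 on 80% of the adapted MI-SCOPE codes and, separately, ICC > .60 on each living-talk and suicide-talk code or summary score that will be analysed. Require this before study sessions are coded. If the analysis uses a strength-of-talk score, as the text of Exploratory Analyses 3-5 suggests, test that score.
2. Report the ICCs for those same variables from the double-coded sample.
3. State what follows if one is .60 or below: retrain the coders and recode, or report that talk analysis as limited by coding reliability.

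The .60 threshold is the protocol's own. It does not remove attenuation: in the illustration, power at exactly .60 is .75 at one-sided .05 and .50 at .01. It does set a floor where none now exists. The cost is a change of wording and some extra practice coding, which may or may not fit within the sixteen training hours; recoding would add work only if the threshold is missed.

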### **Analytical Plan**

**Data Preparation.** All data will be screened for missing data, outliers, non-normality, non-linearity, and non-homoscedasticity. A combination of statistics and graphic representations will be used to complete these screens. Specifically, missing values analyses, descriptive analyses, frequencies, scatter plots and histograms will be used. The assumptions underlying the proposed statistical analyses will also be tested, which may lead to data transformations or the use of more appropriate statistics. Additionally, imbalances in important covariates between randomized groups will be tested at baseline, which may lead to the identification of covariates to be included in the analyses. Findings will be used to fine-tune the analytical plan if statistical assumptions are unmet or model fit is poor. All analyses will be based on an intent-to-treat approach, analyzed as randomized, include all available data, use multiple imputation for missing data if appropriate, and use one-tailed tests with p < .05 as the cutoff for statistical significance. The study is not powered to test exploratory hypotheses, and we therefore do not

expect to detect significant differences between groups. If the analyses are reported as part of the primary RCT, we will use a p-value of .01 to define statistical significance.

**Aim 2:** To evaluate whether MI-SI plus TAU results in significant reductions in suicidal ideation (SI) and increases in treatment engagement when compared to TAU alone.

Primary Hypothesis: Participants who receive MI-SI plus TAU will report greater reductions in SI over follow-up than participants who receive TAU alone.

Primary Analysis 1: An over-dispersion Poisson generalized linear mixed model (GLMM) with maximum likelihood estimation will be used to examine the effect of MI-SI on the severity of SI at 1, 3, and 6 months follow-up. GLMM was chosen because random effects are added to the model to account for repeated measures within subjects. An over-dispersion Poisson GLMM will be used because the SSI is bounded at zero and had a standard deviation larger than the mean at follow-up in our pilot data, indicating over-dispersion. If data do not meet the assumptions of a Poisson distribution, we will use a negative binomial or zero-inflated negative binomial. The benefit of using maximum likelihood estimation is that it yields unbiased estimates in the presence of missing data, if data are missing at random. Because participants may receive one or two sessions of MI-SI, and the change pattern may not be linear over time, we will test sessions of MI-SI, time of assessment, and their interaction in follow-up analyses. As an added measure of clinical significance, we will report the number of participants in each group who fall below the two-point cut-off.

Because the presence of any suicidal behavior (i.e., attempted suicide, interrupted attempts, preparatory behavior) is an important outcome, we will use a mixed effects general logistic model to examine the effect size of MI-SI on the incidence of suicidal behavior as measured by the C-SSRS over follow-up assessments.

Exploratory Hypothesis 1: Participants who receive MI-SI plus TAU will engage in more treatment over follow-up than participants who receive TAU alone.

Exploratory Analysis 1: Multivariable logistic regression will be used to examine the effect of MI-SI on treatment engagement. The Hosmer-Lemeshow statistic will be used to evaluate model fit, and odds ratios with 95% confidence intervals will be derived using the method of maximum likelihood.  Because participants may receive one or two sessions of MI-SI, we will conduct a sensitivity analysis examining the number of MI-SI sessions as a predictor of treatment engagement. Because this is an underpowered exploratory analysis, we will also conduct secondary analyses using other definitions of treatment engagement such as number of sessions attended.

We will also examine the impact of the intervention on use of the Safety Plan coping strategies. To test treatment differences, we will use a multivariable logistic regression.

Exploratory Hypothesis 2: Treatment engagement over follow-up will partially mediate the impact of MI-SI on SI.

Exploratory Analysis 2: Analyses will examine treatment engagement as a mediator of the impact of MI-SI plus TAU on SI. Treatment engagement is expected to partially mediate the relationship between randomization to the MI-SI group and SI over follow-up, such that the relationship is smaller but the effect size is still significant. Structural equation modeling (SEM) will be used to examine this potential mediation relationship. SEM is a method for creating latent

variables and identifying and describing causal relationships between the latent variables. We decided to use SEM because it simultaneously tests independent and conjoint relationships and uses latent variables, which minimizes measurement error. The model will consist of both latent and observed variables. Latent variables will be used for variables such as SI (via the SSI) to fit the data for this population. Observed variables will be used for variables such as randomization to MI-SI and treatment engagement (via the TSR). Because these analyses will be underpowered, this exploration will be based on effect sizes rather than statistical significance. Furthermore, we will also conduct more basic mediation regression models as secondary analyses.

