**Baseline Assessment.** To describe the sample, all participants will complete the baseline assessment that will include measures of depression, substance use disorders, PTSD, and trait anxiety as they have been found to increase risk for suicide in Veterans,  treatment engagement which is associated with suicide after discharge from psychiatric hospitalization,  insomnia which may be associated with suicide risk in Veterans,  anger is associated with increased suicide risk and may impact the effectiveness of MI based interventions for Veterans,  and previous suicidal behavior which is a robust predictor of suicide.  Although there are no measures of motivation to live, we are also interested in piloting a motivation to live measure as a potential risk factor. We are also adding three measures that assess mechanisms through which MI-SI may work and therefore serve as short-term outcomes. They will be used to describe the sample and may be controlled for in the analyses if there are differences between conditions.

- 1. Depression (9 items): The Physicians Health Questionnaire (PHQ-9)  is a reliable and valid self-report assessment of depressive symptoms that is used by VA. 
- 2. PTSD (17 items): The PTSD Checklist Civilian Version (PCL-C)  $^{58}$  is a reliable and valid self-report assessment of PTSD symptoms  $^{59}$  that is used with Veterans.  $^{60}$

- 3. Anxiety (21 items): The Beck Anxiety Inventory (BAI)  $^{61}$  is a reliable and valid self-report measure of anxiety.
- 4. Alcohol Use Disorders (10 items): Alcohol Use Disorders Identification Test (AUDIT)  $^{62}$  is a self-report measure designed to assess hazardous alcohol use that is reliable and valid in Veterans.  $^{63}$
- 5. Drug Abuse (10 items): A reliable and valid 10-item short-form of the Drug Abuse Screening Test (DAST)  $^{64}$  will be used to assess non-prescription drug abuse, not including alcohol abuse. The DAST has been used with Veterans.  $^{65}$
- 6. Substance Use Frequency past 90 days / Drug of Choice (12 items): The Substance Use Frequency Form (SUFF) is a measure that was developed by [name] to assess substance use frequency and drug of choice. It is based on questions commonly used in the substance abuse literature.  $^{66}$

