- 7. Drug Use Consequences (15 items): The Inventory of Drug Use Consequences (INDUC)  $^{67}$  is the gold-standard self-report assessment of substance-related consequences in the past 90 days. It has been used with Veterans.  $^{68}$
- 8. Insomnia (7 items): The Insomnia Severity Index (ISI) is a widely used, reliable and valid self-report instrument of sleep difficulty. 
- 9. Anger (5 items): The Lifetime History of Aggression Questionnaire (LHAQ) is a brief, valid, and reliable measure of aggression .
- 10. Treatment Engagement (26 items): Treatment engagement will be measured using the Alcohol and Drug Services, Medication, Medical Services, and Psychological Services sections of the Treatment Services Review (TSR-6) which have been shown to be both reliable and valid. 71 The TSR-6 will be used at baseline and the 1, 3 and 6 month follow-ups to inquire about use of these services. The baseline assessment will be used to compare engagement in psychological and alcohol and drug service use between groups to assess whether it needs to be accounted for in the analyses. Engagement in psychological and alcohol and drug services will also be assessed at each follow-up assessment and used as an exploratory outcome. Treatment engagement will be treated as a dichotomous outcome, and will be defined according to the Substance Abuse and Mental Health Services Administration (SAHMSA) Washington's Circle standards, 72 which have been adopted by VA. 73 For residential patients and inpatients, treatment engagement is defined as attending two outpatient visits in the 30-days after discharge. In Veterans with substance use disorders, this measure of treatment engagement has been found to be associated with treatment outcome 74 and hospitalization in those with a suicide attempt history. 75 In Veterans discharged from psychiatric hospitalization, completing two outpatient sessions in at least two of the six months after discharge has also been found to be associated with suicide. 1
- 11. Suicidal Behavior (18 items): The Colombia Suicide Severity Rating Scale (C-SSRS)  will be used to assess history of suicidal behavior at baseline and at follow-up assessment. It has been mandated for use in medication trials by the FDA. 

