In session 1, clinicians will attempt to proceed through all three phases. In session 2, clinicians will summarize session one and use patients' response to the summary to decide which phase to return to. If patients are in phase 3, clinicians' will help them refine and reinforce their plan. If they are undecided about mental health or substance abuse treatment, clinicians will return to phases 1 or 2 and explore reasons against engaging in treatment, build the motivation to engage in it, and strengthen their commitment to do so. Veterans in the MI-SI condition will also complete one telephone booster MI-SI session (30-50 mins.) within one-month (weeks 3-6) after discharge. Telephone contact within one month after discharge is a component of treatments that have been found to reduce risk for suicidal behavior and will be used to increase the dosage of MI-SI.  Participants will be provided a handout with the scheduled telephone follow-up and therapist contact information. Telephone sessions will consist of an abbreviated MI-SI interview following the strategy of session 2. For telephone sessions, phase 3 will include a review of their mental health and substance abuse treatment and explore alternative or additional treatments if they are called for. All MI-SI sessions will also be recorded for coding.

TAU. All patients that are admitted to the acute psychiatric unit receive standard inpatient treatment that includes medication management, case management, meals and a bed, and milieu therapy consisting of creative and social activities (e.g., crafts, video games, karaoke). Families of Veterans may also receive education concerning the Veteran's problems to create a supportive home environment. Suicidal patients receive additional services. VA mental health clinicians are required to complete a Safety Plan with all suicidal Veterans, and each VAMC has hired a Suicide Prevention Coordinator (SPC) to oversee the care of high-risk patients. The Syracuse VAMC also hired Case Managers to help meet essential living needs of suicidal Veterans. SPCs and Case Managers work collaboratively to help suicidal patients transition from inpatient to outpatient treatment. Chart reviews will provide a detailed description of the components of TAU that each participant receives so that suicide-specific TAU can be described in detail. Suicide-related TAU will be controlled for in analyses if differences are observed between conditions.

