Power Analysis: Recruitment will provide data on 112 participants. Assuming a retention rate of 80%, data on 90 participants will be available at the 6 month follow-up. To estimate the statistical power afforded by 90 participants for the severity of SSI, power analyses were conducted using STATA 11 101 "sampsi2" package, which uses calculations based on Frison and Pocock model. 102 Specifying method of analysis (change), number of baseline assessments (1), number of post assessments (3), correlation between baseline and follow-up scores (r = .50), correlation between follow-up scores (r = .70), and standard deviation (sd = 8.4) for the outcome variable using Frison and Pocock's recommendations and our pilot data. we would have .94 power to identify a 5-point difference in mean SSI scores between treatment arms, .81 power to identify a 4-point difference, and .60 power to identify a 3-point difference. The study would therefore be adequately powered to find an effect size of .5 for the primary outcome. If there is concern that the experimental intervention caused harm and the trial is not stopped, we will conduct two-sided analyses instead of the one-sided analyses we proposed. Power analyses suggest we will have .88 power to identify a 5-point difference, .71 power for a 4-point difference, and .47 power for a 3-point difference with the proposed 90 participants (45 in each group), indicating that the trial will still be fairly well powered.

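### Covariates enter the analyses only if the arms differ, so selection rests on chance imbalance, the primary model is not fixed in advance, and most of the power gain from fixed adjustment is forgone

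*Combined protocol and SAP*

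**What the plan says.** Four places in the combined protocol and SAP make adjustment depend on how the arms compare.

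- **Analytical Plan, Data Preparation:** "imbalances in important covariates between randomized groups will be tested at baseline, which may lead to the identification of covariates to be included".
- **General Procedures, Baseline Assessment (introduction):** the listed measures "may be controlled for in the analyses if there are differences between conditions".
- **Same section, item 10 (Treatment Engagement):** one stated purpose of the baseline data is this: "compare engagement in psychological and alcohol and drug service use between groups to assess whether it needs to be accounted for in the analyses".
- **Treatment Conditions, TAU:** "Suicide-related TAU will be controlled for in analyses if differences are observed between conditions".

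None of them names the test, the threshold or the covariates. Primary Analysis 1 is an over-dispersed Poisson mixed model to "examine the effect of MI-SI on the severity of SI at 1, 3, and 6 months follow-up". It lists neither baseline SSI nor the randomisation stratum as a term, although the Randomization paragraph stratifies on SSI at a cut of 24. The primary test is one-sided at .05.

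**The concern.** In a properly randomised trial, any baseline difference between arms has arisen by chance. A test of that difference does not show whether the variable predicts follow-up SSI, and prediction is what makes adjustment worthwhile. Under the rule a strong predictor is left out when it happens to be balanced, and a weak one enters when it is not.

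Two things are at stake.

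- **Prespecification.** The covariates of the primary model are unknown until the arms have been compared, and the word "may" leaves inclusion to judgement at that point.
- **Precision.** A screen that admits a covariate only in the few trials where it is imbalanced gives up most of what routine adjustment would add.

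The TAU rule raises a further problem. The Chart Reviews paragraph has the follow-up review cover the 6 months after discharge and record use of suicide prevention services, so a difference in TAU may be a consequence of the intervention. The plan itself intends to examine the effect of MI-SI on Safety Plan use and on treatment engagement. Adjusting for such care could remove part of the effect being estimated.

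**Working it through.** **Inputs.** From Power Analysis: 45 per arm, SD 8.4, baseline-to-follow-up correlation .50, correlation between follow-ups .70, one baseline and three post-baseline measures, and the change method. From Data Preparation: one-sided .05. Assumed, because the plan gives none: a two-sided .05 screen for imbalance.

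**1. Reproduce the plan's power.** Frison-Pocock variance factors:
- follow-up mean only: (1 + 2×.70)/3 = .80
- change from baseline: .80 + 1 − 2×.50 = .80
- adjusted for baseline (ANCOVA): .80 − .50² = .55

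Power = Φ(δ / [8.4 × √factor × √(2/45)] − 1.645). For change at 4 points, the standard error is 8.4 × √.80 × √(2/45) = 1.584, so 4/1.584 − 1.645 = .88 and power is .811.

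| Difference | Plan | Reproduced (change) | Fixed baseline adjustment |
|---|---|---|---|
| 5 points | .94 | .935 | .985 |
| 4 points | .81 | .811 | .919 |
| 3 points | .60 | .598 | .739 |

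The plan's figures reproduce. At r = .50 the change and follow-up-only factors are both .80, so the stated power does not depend on covariate adjustment.

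**2. Apply the rule to baseline SSI.** Simulated normal trials, 4 points, 20,000 per scenario:

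| Randomisation | Correlation | Unadjusted | Test-then-adjust | Fixed adjustment |
|---|---|---|---|---|
| Simple | .3 | .803 | .807 | .839 |
| Simple | .5 | .807 | .820 | .916 |
| Simple | .7 | .801 | .824 | .991 |
| Stratified, blocks of 4 and 6 | .5 | .833 | .833 | .916 |

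At r = .5 under simple randomisation the rule keeps about .01 of a gain of about .11, roughly a tenth. Under the planned stratification, baseline SSI fails the balance test in only about 0.1% of trials, so practically none of the gain is kept. A looser screen at p < .20 (r = .5, simple randomisation) gives .845, about a third of the gain.

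**3. Type I error.** In the single-covariate check at r = .5, test-then-adjust rejects in about .044 of null trials under simple randomisation and about .033 under stratification, against .050 with fixed adjustment. The departure is conservative.

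**4. Other covariates.** The documents give no correlation with follow-up SSI for any of them, so these values are assumptions. With a single outcome and a difference of 4/8.4 = .476 SD, power = Φ(.476 / [√(1 − r²) × √(2/45)] − 1.645):
- r = 0: .730
- r = .1: .734 (gain about 0)
- r = .3: .765 (gain about .03)
- r = .5: .832 (gain about .10; simulations give .08 to .10)

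Once baseline SSI is in the model, the factor is .55 × (1 − p²) for an assumed partial correlation p. Power at 4 points is .922, .928 and .939 for p = .1, .2 and .3, against .919 without the extra covariate. The added gain is at most about .02 over that range.

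**5. Chance of finding something imbalanced.** The Baseline Assessment list has 16 measures. If they were independent and tested at .05, the chance of at least one flag is 1 − .95¹⁶ = .56. With an assumed common correlation of .3 or .5 it falls to about .48 or .37.

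**The case against.** The strongest reply is that the practical loss may be small. The plan limits the tests to covariates it calls important and says only that they may be included. Most of the pool was chosen as suicide risk factors, so it is not arbitrary. The only correlation the documents support is the .50 for baseline SSI, and gains from PHQ-9 or prior attempts could be close to zero once SSI is adjusted for. The .56 is an upper-end figure, because the depression, PTSD, anxiety and insomnia scales, and likewise the substance use scales, are likely to be correlated. The figures are also normal approximations to a planned Poisson mixed model. All of this stands, and it limits the size of the point. It does not rescue the criterion: within any pool, selection is still by imbalance, and the list is still not fixed.

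Three stronger readings are tempting, and the documents do not support them.

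- **The trial loses most of its power.** It does not. Power at 4 points stays at about .82 or .83, and the figures in Power Analysis reproduce without covariate adjustment. This is a forgone gain, not a shortfall.
- **The rule inflates false positives.** In the check above it is nominal to conservative.
- **Baseline SSI is certain to be absent from the primary model.** The plan does not list it, but it does not exclude it either. If SSI entered as a change score or a repeated measure, the loss could differ: at r = .50 a change score gains nothing over follow-up alone, but at r = .7 it would recover most of the gain.

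Item 10 may also concern only the exploratory engagement outcome, since its wording does not say which analyses are meant.

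**Conclusion.** The point holds as one of prespecification and forgone precision. Covariates are admitted according to chance differences or, for TAU, possibly according to care received after randomisation, and the primary model is not settled until the arms have been compared. For baseline SSI, at the plan's own r = .50, the rule gives up roughly nine tenths of a gain of about .11 in power at 4 points, and practically all of it under the planned stratification. This rests on a .05 screen, a normal approximation and 45 analysed per arm. For other covariates the size cannot be taken from the documents: about 0 to .10 over assumed correlations of .1 to .5, and less once baseline SSI is in the model. The plan should be changed, but its stated power and its error rate are not in question on this ground.

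**What to change.** 1. Delete the imbalance-test rule from Data Preparation, from the Baseline Assessment introduction and from item 10.
2. In Primary Analysis 1, name baseline SSI and the randomisation stratum, with a short list of prognostic baseline covariates already collected (for example PHQ-9 and prior suicide attempt). Fix the list before any comparison of the arms and include it regardless of balance.
3. Report baseline values by arm descriptively, without p-values.
4. Keep any model prompted by an observed imbalance as a labelled sensitivity analysis.
5. In the TAU paragraph, replace the adjustment rule with a description of TAU by arm, and do not adjust the primary analysis for TAU received after randomisation.

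The cost is analysis-plan wording only. Each term uses one degree of freedom: two for the example covariates and two for baseline SSI and the stratum, from about 90 participants. The sponsor also gives up the freedom to add covariates to the primary model later. No data collection changes.
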